- Clinician who usually monitors given patient is unaware of the group patient is allocated to, or the dose prescribed to a patient at Visit 1.
- Outcomes measured:
 1. Clinical questionnaires
 2. Anthropometric measurements
 3. Cardiological assessment
 4. Serum samples for biochemical analyses
 5. Plasma samples to reconfirm TDM findings in V_k

Week 6

Visit 2 (V2) – *Identical to the standard protocol*

- Final visit of the trial and the end of the follow-up.
- Outcomes measured:
 1. Clinical questionnaires
 2. Anthropometric measurements
 3. Cardiological assessment
 4. Serum samples for biochemical analyses
 5. Plasma samples to reconfirm TDM findings in V_k and V1 for Standard dosing group, and to determine whether personalized dose is optimal for the patients in Personalized dosing group.

Hypotheses:

- 1) More than one quarter of participants will be overdosed or underdosed under standard escitalopram dosing regimen (10 mg/day), as determined by TDM data 2 weeks after the beginning of the therapy.
- 2) Participants with escitalopram steady state plasma concentration outside the therapeutic window (“Adjusted dose” group) will experience reduced efficacy and more severe side effects of escitalopram therapy before dose personalization (at V1) compared to the participants with escitalopram levels within therapeutic window (“Standard dose” group) at standard dosing.
- 3) Participants with escitalopram steady state plasma concentration outside the therapeutic window (“Adjusted dose” group) will show improved efficacy and less severe side effects of escitalopram therapy after dose personalization (at V2) as compared to before (at V1), and will reach clinical outcomes comparable to the “Standard dose” group (at V2).

- 4) Decisions on whether to use personalized or standard dosing, and how to adjust personalized dose based on TDM data could have been determined before the beginning of the treatment using predictive model which, besides other predictors also includes *CYP2C19* genotyping data.

Statistical Analysis Plan

Primary outcomes:

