Other primary outcome we will use to quantify changes in clinical outcomes between test groups will be severity of the treatment side effects measured using clinician reported UKU (*Udvalg for Kliniske Undersogelser*) side effect rating scale. UKU scale rates 48 potential adverse reactions with intensity score ranging from 0 to 3 where score 3 signifies maximal intensity and score 0 signifies absence of the adverse reaction. Adverse drug reaction intensity scores for all 48 adverse reactions monitored with UKU scale will be measured at weeks 4 (V1) and 8 (V2) after the initiation of the escitalopram therapy. Due to large number of comparisons, significance measures will be adjusted using False Discovery Rate (FDR) correction. Absolute values of all 48 Adverse reaction scores will be compared between test groups and between two time points using mixed model analysis of covariance (Mixed ANCOVA) where variables will be assigned as follows:

1. Dependent variable: Adverse drug reaction score for the given adverse reaction measured by UKU scale
2. Independent variable - Fixed factor: Test group (Personalized vs Standard dosing)
3. Independent variable - Repeated measurements: Visit (Visit 1 vs Visit 2)
4. Covariables: Age, Sex (Male=0, Female=1), Smoking status (0=Non-smoker, 1=Smoker), Alcohol consumption (0=No, 1=Yes), Coffee consumption (0=No, 1=Yes), Use of psychoactive substances (0=No, 1=Yes), Metabolic syndrome (0=No, 1=Yes), Creatinine clearance, AST/ALT ratio.

Positive outcome: interaction between group and visit is significant ($\alpha=0.05$)

Alternatively, proportions of patients with intensity score greater than 0 (UKU scale intensity score >0 signifies the presence of the given adverse reaction) will be compared between the groups for all 48 adverse effect monitored with UKU scale at two time points: 4 weeks after the enrolment (V1) and 8 weeks after the enrolment (V2). Due to large number of comparisons, significance measures will be adjusted using False Discovery Rate (FDR) correction. Proportion of individuals in two test groups affected with the given adverse reaction will be compared using binary logistic regression analysis separately for visit V1 and visit V2 as follows:

1. Dependent variable: Frequency of the individuals affected with the given adverse drug reaction measured by UKU scale

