2. Covariables: Test group (Personalized vs Standard dosing), Age, Sex (Male=0, Female=1), Smoking status (0=Non-smoker, 1=Smoker), Alcohol consumption (0=No, 1=Yes), Coffee consumption (0=No, 1=Yes), Use of psychoactive substances (0=No, 1=Yes), Metabolic syndrome (0=No, 1=Yes), Creatinine clearance, AST/ALT ratio.

Positive outcome: Test group is a significant factor ($\alpha=0.05$)

Secondary outcomes:

Retrospective TDM data on 2087 patients taking escitalopram [Jukić 2018] suggests that, in the clinical setting, about 40% of patients are expected to have their plasma escitalopram concentrations under the lower limit of the therapeutic window (25 ng/ml), and for about 10% of patients we expect to have plasma escitalopram levels above the upper limit of the therapeutic window (50 ng/ml). One of our aims is to try to confirm these findings using prospective study design which allows for the better control of the confounding factors compared to the retrospective data. Number of the patients with plasma escitalopram levels outside the therapeutic window under standard dosing regimen (10 mg/day) will be assessed using TDM data at Mid-Visit (VK), 2 weeks after the beginning of the therapy.

Big disadvantage of TDM guided establishment of the optimal drug exposure in the given patient is that it takes 4 weeks to personalize escitalopram dose and 2 more weeks to achieve optimal steady state drug concentrations. Alternative approach would be to build model that could predict optimal dose for every patient even before the initiation of the treatment. This model would have to include patient data on factors that could impact escitalopram exposure such as body weight, liver and kidney functions and genotype for the *CYP2C19* gene which is responsible for the interindividual variability in the rate of escitalopram metabolism in liver [Jukić 2018]. After all participants have finished the trial we will retrospectively build model using data collected during the trial, and then validate our model comparing it to the TDM method of dose personalization. For this purpose, all patients will be genotyped for *CYP2C19* gene and divided into 4 groups based on the enzymatic capacity of CYP2C19 enzyme:

1. Poor metabolizer (PM): Carries *2/*2, *2/*3 or *3/*3 *CYP2C19* genotype. Almost absent CYP2C19 enzyme activity
2. Intermediate metabolizer (IM): Carries *1/*2 or *1/*3 *CYP2C19* genotype. Reduced CYP2C19 enzyme activity

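### No planned UKU test with a success rule compares the full 0-3 score between groups at V1 or V2, so the severity claim in hypothesis 2 has no direct test

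*Combined protocol and SAP*

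**What the plan says.** Hypothesis 2 (section Hypotheses) is a between-group claim at one visit: patients outside the therapeutic window "will experience reduced efficacy and more severe side effects of escitalopram therapy before dose personalization (at V1"), compared with patients inside it. Hypothesis 3 adds that side effects in the Adjusted group lessen from V1 to V2 and that the groups are comparable at V2.

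The SAP, under Primary outcomes, makes side-effect severity a primary outcome. Each of 48 UKU items has an "intensity score ranging from 0 to 3 where score 3 signifies maximal intensity and score 0 signifies absence of the adverse reaction". Two analyses follow, each with FDR correction:

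- **Full score.** "Absolute values of all 48 Adverse reaction scores will be compared between test groups and between two time points", by mixed ANCOVA with test group as fixed factor and visit as repeated factor. The success rule is "Positive outcome: interaction between group and visit is significant". No group contrast at V1 or at V2 is named.
- **Presence.** After the word that opens "Alternatively, proportions of patients with intensity score greater than 0", score >0 is "compared using binary logistic regression analysis separately for visit V1 and visit V2". The success rule is "Positive outcome: Test group is a significant factor".

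The SAP does not say whether the second analysis supplements the first or stands in for it.

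**The concern.** The hypothesis, the scale and the tests do not line up. Hypothesis 2 concerns severity, between groups, at V1. The full-score analysis is judged on whether the group difference changes between visits. The visit-specific analysis is judged on whether a reaction is present at all. Neither success rule asks whether the groups differ in severity at V1.

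Two errors become possible on a primary outcome. A real V1 intensity difference that lasts to V2 gives no interaction and, if prevalence is equal, no signal in the logistic model. At V2, a remaining intensity difference can pass as comparable because similar proportions score above 0.

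**Working it through.** **Inputs from the documents.** Items scored 0-3; 48 items; alpha 0.05 (sidedness not stated, two-sided assumed). Secondary outcomes expects about 40% of patients below and 10% above the window, so about 40 + 10 = 50% in the Adjusted group, a 1:1 split. The documents state no sample size, UKU item rates or effect size, so there is no plan figure to reproduce.

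**Assumed inputs.** 100 per group; a common odds ratio of 2 across the three cut-points; six Standard-group distributions; no covariates; alpha 0.05 per item before FDR correction.

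**1. What the interaction measures.** Let d1 and d2 be the group differences in mean score at V1 and V2. The interaction is d1 - d2. It equals d1 if d2 = 0, and is zero if d2 = d1, however large d1 is. Simulation with Standard scores 40/30/20/10% at both visits, odds ratio 2 at V1 and an assumed latent within-patient correlation of 0.5:

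| Odds ratio at V2 | Interaction power | Full-score V1 contrast power |
|---|---|---|
| 2 (persists) | 5% | 77% |
| 1.4 (about halves) | 26% | 77% |
| 1 (resolves) | 73% | 77% |

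**2. What the >0 cut costs: one case by hand.** Standard 40/30/20/10. The odds of scoring >0 are 0.60/0.40 = 1.5; doubled, 3.0, so 75% in the Adjusted group. Shifting the other cut-points likewise gives 25.0/28.8/28.0/18.2.

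- Two-proportion power, 0.60 vs 0.75: null SE = √(2 × 0.675 × 0.325/100) = 0.0662; alternative SE = √((0.60 × 0.40 + 0.75 × 0.25)/100) = 0.0654; z = (0.15 - 1.96 × 0.0662)/0.0654 = 0.31, so power is about 62% (63% simulated).
- Efficiency of the cut relative to the ordinal test is 3p(1 - p)/(1 - Σpᵢ³), where the pᵢ are category probabilities averaged over the groups and p is the averaged probability of score 0. The averages are 0.325, 0.294, 0.240, 0.141. So 3 × 0.325 × 0.675 = 0.658, Σpᵢ³ = 0.076, and 0.658/0.924 = 0.71. The cut needs 1/0.71, or about 1.4 times, as many patients.

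**3. All six distributions** (20,000 simulated trials each; two-proportion test on >0 against the tie-corrected Wilcoxon test, the score test of the unadjusted proportional-odds model):

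| Standard group 0/1/2/3, % | Score >0 | Power, >0 cut | Power, full score | Efficiency |
|---|---|---|---|---|
| 80/12/6/2 | 20% | 57% | 58% | 0.98 |
| 60/22/13/5 | 40% | 70% | 73% | 0.89 |
| 50/25/17/8 | 50% | 68% | 77% | 0.81 |
| 40/30/20/10 | 60% | 63% | 77% | 0.71 |
| 30/35/25/10 | 70% | 54% | 77% | 0.59 |
| 20/35/30/15 | 80% | 42% | 77% | 0.43 |

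The loss is about 1 to 3 points below 50% prevalence and about 8 to 35 points from 50% upward.

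**4. Intensity only.** Standard 30/45/20/5 against Adjusted 30/20/35/15, with 70% affected in both: the cut has about 5% power (the type I error rate), the ordinal test about 67%.

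**5. Multiplicity.** At the strictest FDR threshold, 0.05/48 = 0.00104, both powers fall but the gap remains: 15% against 27% for 40/30/20/10.

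**The case against.** A reader might infer that the plan discards severity and tests side effects on presence alone. The documents do not support that. The mixed ANCOVA is listed first, keeps the 0-3 score for all 48 items and includes test group as a factor; nothing says the >0 analysis replaces it. If hypotheses 2 and 3 both hold, so that the groups differ at V1 and are alike at V2, the interaction recovers most of the V1 signal: 66-74% power for the five distributions with at least 40% prevalence (48% for 80/12/6/2), and 73% in the intensity-only case. This stands, and it confines the gap to differences that persist, wholly or partly, to V2. It does not close the gap, because convergence at V2 is what hypothesis 3 sets out to show.

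A reader might also take the power loss as a property of this trial. It is not. No document shows that any item reaches 50% prevalence, and an odds ratio of 2 for the whole Adjusted group is an assumption. By the plan's own expectation, only 10/(40 + 10) = one fifth of that group is overdosed. If only that fifth carries the odds ratio of 2, power at 100 per group is 6-8% for the cut and about 8% for the full score, a gap of about 2 points or less. If underdosed patients instead have an odds ratio of 0.67, the cut is slightly ahead in five of the six distributions. The ordinal test is therefore not better under every pattern.

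Finally, whether a reaction is present is a legitimate question, and sparse upper categories may prevent some ordinal fits. Both points argue against dropping the >0 analysis, not against adding a severity test.

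**Conclusion.** The gap holds on the text alone: no UKU test with a success rule compares the 0-3 score between groups at V1 or at V2. The interaction misses a V1 difference that persists unchanged, and the logistic model cannot see intensity among affected patients.

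The size is illustrative. It rests on an assumed sample size, item distributions and odds ratio, unadjusted tests and, for the interaction, an assumed correlation of 0.5. Under those inputs the loss runs from negligible for uncommon items to large for common ones, and is complete when only intensity differs. It nearly vanishes if only overdosed patients are affected. The case for change is that the trial should be able to test its own hypothesis with data it already collects; it does not depend on a promised power gain.

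**What to change.** In the UKU part of Primary outcomes:

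- Make the test of the side-effect half of hypothesis 2, and the V2 comparison, a between-group comparison of the 0-3 item score at each visit, with the UKU covariates already listed and the same FDR correction.
- Use a proportional-odds model. Where the upper categories are too sparse to fit, use the V1 and V2 group contrasts from the mixed model already planned, and set that sparsity rule in advance.
- Keep the >0 logistic regression as a supporting analysis of presence, and state that it supplements the full-score analysis and does not replace it.
- Keep the interaction as the test of change between visits.

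The cost is SAP wording and one additional model per item and visit (48 × 2 = 96 fits), with no new data or patients. A common odds ratio is slightly harder to explain than a difference in prevalence and rests on a proportional-odds summary; the retained >0 analysis helps the clinical reader.

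### The 96 UKU presence/absence logistic models name no estimator, no test of the group term and no rule for sparse items, so the group comparison is unreliable for uncommon reactions under the usual defaults

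*Combined protocol and SAP*

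**What the plan says.** Under Primary outcomes, the Statistical Analysis Plan first compares the UKU item scores by mixed ANCOVA. It then gives an alternative analysis of presence or absence, in which proportions "will be compared between the groups for all 48 adverse effect monitored with UKU scale at two time points". The event is a score above zero: "UKU scale intensity score >0 signifies the presence of the given adverse reaction". The proportions "will be compared using binary logistic regression analysis separately for visit V1 and visit V2".

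Each model contains test group, age, sex, smoking, alcohol and coffee, followed by "Use of psychoactive substances (0=No, 1=Yes), Metabolic syndrome (0=No, 1=Yes), Creatinine clearance, AST/ALT ratio". The success rule is "Positive outcome: Test group is a significant factor" at alpha 0.05, and "significance measures will be adjusted using False Discovery Rate (FDR) correction".

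The plan does not name the estimator, the test of the group term (Wald, likelihood ratio or score), a minimum event count, or what happens when a cell is empty or a fit does not converge. The documents give no sample size and no expected item frequencies.

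**The concern.** Binary logistic regression without qualification is normally fitted by maximum likelihood, and the default coefficient table reports Wald p-values. Ten terms is a large model for a reaction that only a few participants report. If no one in one group has the reaction, the group log-odds ratio has no finite estimate and the Wald test loses its meaning, although the contrast may be strong. Using the likelihood-ratio test from the same fit avoids that failure but is untrustworthy in the other direction when events are few.

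What is at stake is hypothesis 2, which predicts more severe side effects in the Adjusted dose group at V1, before personalisation. The separate V1 logistic models are the only UKU analysis whose stated success rule tests a group difference at V1. For uncommon reactions, the answer would depend on a software default that the plan leaves open.

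**Working it through.** **Inputs from the documents.** 48 items × 2 visits = 96 models. Terms per model: 1 (group) + 9 covariates = 10. Expected group split: Secondary outcomes expects about 40% of patients below the window and 10% above it, so 40% + 10% = 50% Adjusted and 50% Standard. There is no figure in the plan to reproduce.

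**Assumed inputs.** N of 100, 150 and 200; item rates of 1% to 20%; binary covariate prevalences; three continuous covariates; unadjusted alpha 0.05.

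**Step 1: one table with an empty cell, group term only, 8/75 versus 0/75.**
- Maximum likelihood: log-odds ratio = ln[(8 × 75)/(67 × 0)], which is infinite. The fitted standard error grows without limit, and Wald p is about 1.0.
- Likelihood ratio: with group, 8 ln(8/75) + 67 ln(67/75) = −25.462. Without group, 8 ln(8/150) + 142 ln(142/150) = −31.232. Twice the difference is 11.54 on 1 df, p=0.0007.
- Fisher exact: p=0.006.
- Firth: log-odds ratio = ln[(8.5 × 75.5)/(67.5 × 0.5)] = 2.95, which is finite; profile penalised-likelihood p=0.003.

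**Step 2: the same failure with all ten terms.** At 0/50 versus 10/50, Wald gave p<0.05 in 0% of 200 simulated data sets and the likelihood-ratio test in 100%.

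**Step 3: does the likelihood-ratio test hold its level?** In ten-term simulations with no group effect, at item rates of 2–5%, it rejected about 9–19% of nulls across the three values of N. A repeat with 2,000 data sets per cell (rarest covariate 8%) gave 13–14% at a 2% rate. At a 5% rate it gave 13%, 9% and 6% for N of 100, 150 and 200. The excess is clear where events are fewest and fades as they accumulate. Firth rejected 0.5–6.5% of nulls.

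**Step 4: power in the ten-term model at true rates of 1% versus 12%.**

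| N | Wald | Firth |
|---|---|---|
| 100 | 13% | 55% |
| 150 | 33% | 79% |
| 200 | 53% | 91% |

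**Step 5: how far the problem reaches.** With n per group and common rate p, the chance of no events in at least one group is 1 − (1 − (1 − p)^n)². For n=50:
- p=2%: 0.98^50 = 0.364, giving 1 − 0.636² = 60%.
- p=5%: 0.95^50 = 0.077, giving 1 − 0.923² = 15%.
- p=10%: 0.90^50 = 0.005, giving 1%.

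In the full ten-term model with no group effect, linear-programming checks gave the chance that the group coefficient itself has no finite estimate. At a 5% rate this was 19–26% for N=100 (depending on the assumed covariate prevalences), 3–5% for N=150 and 2% for N=200. At 10% or more with N of 150 or more it was essentially nil. Estimates can be weak even when finite: at N=100 and a 5% rate there are 100 × 0.05 / 10 = 0.5 events per term.

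**Step 6: limit of these figures.** They are before FDR adjustment, and the plan does not name the FDR procedure or the family. If Benjamini-Hochberg covered all 96 tests, a lone signal would need p ≤ 0.05/96 = 0.00052. None of the p-values in Step 1 would pass on its own.

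**The case against.** The plan never says maximum likelihood or Wald. A reader might infer that it prescribes a method that fails, but the documents support only that the choice is open. The likelihood-ratio test from an ordinary fit finds the 8/75 versus 0/75 contrast easily, so the claim that the clearest signals must come out non-significant is true of the Wald test alone. Both points stand. They do not settle the matter, because the likelihood-ratio test is anti-conservative for the rarer items in a ten-term model.

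A reader might also infer that most models for uncommon items break down. In one check, some coefficient had no finite estimate in 87%, 66% and 59% of data sets at a 5% rate (N of 100, 150 and 200). The corresponding figures for the group coefficient were 19%, 3% and 2%. The difference mostly reflects rare covariates, and separation on a covariate alone leaves the group term estimable. The larger figures should not be quoted as failure of the group test.

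Finally, the logistic analysis is introduced as an alternative to a mixed ANCOVA of the same items, which does not suffer from separation. So it does not follow that a real excess would go unreported throughout. But the mixed ANCOVA's stated success rule is the group-by-visit interaction, which is not the V1 group comparison that hypothesis 2 needs.

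**Conclusion.** The point holds in a limited form. For uncommon reactions, neither default test of the planned model is satisfactory. Wald loses strong contrasts (13/33/53% power against 55/79/91% for Firth at 1% versus 12%), and the likelihood-ratio test rejects too often under the null, mainly at the lowest event counts. Firth keeps null rejection at or near 5% or below.

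The direction of these results follows from the algebra of empty cells and from small event counts. The sizes rest on assumed N, item rates and covariate prevalences, none of which the documents give. It would go too far to say that the problem holds for any plausible N and item rate: under the null, the group term is almost never separated at 10% or more with N of 150 or more. This is a cheap improvement to a primary-outcome analysis and does not show that the UKU analysis as a whole fails.

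**What to change.** State in the Statistical Analysis Plan that the UKU presence/absence models will be fitted by Firth-penalised logistic regression, with profile penalised-likelihood p-values for the test-group term. Keep the same covariates and the same FDR step. Fix this before the outcome data are seen.

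The cost is one sentence and standard software. The downside is slight shrinkage of the estimates for common items.

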3. Normal metabolizer (NM): Carries *1/*1 *CYP2C19* genotype. Normal CYP2C19 enzyme activity
4. Ultra rapid metabolizer: Carries *1/*17 or *17/*17 *CYP2C19* genotype. Increased CYP2C19 enzyme activity

Multiple linear regression model will be build using selected variables:

1. Dependent variable: Plasma escitalopram concentrations at Week 2 (Vk) after the initiation of the treatment
2. Independent variables: Body mass index, PM status (0=Yes, 1=No), IM status (0=Yes, 1=No), NM status (0=Yes, 1=No), UM status (0=Yes, 1=No), Creatinine clearance, AST/ALT ratio

Other outcome measures/observations:

To further validate our primary outcome measures: escitalopram treatment efficacy and severity of adverse effects, we will use Clinical Global Impression (CGI) scales. Scores will be determined for all 3 CGI scales: for Severity of illness (CGI-S) scale at baseline, visit 1 and visit 2, and for Global improvement (CGI-I) scale and for Efficacy Index (CGI-E) at visits 1 and 2. Differences in all 3 CGI scales between visits 1 and 2 will be compared between test groups separately using ANCOVA tests with the equivalent sets of covariates to the ones used for HAM-D scale.

In all patients at baseline and at visits 1 and 2, electrocardiography will be performed in order to monitor potential QT interval prolongation. We will test for correlation between QT interval length and escitalopram plasma levels at various visits, and also we will compare changes in QT interval length between visit 1 and visit 2 in both test groups using mixed ANCOVA test adjusting for the baseline QT length.

Due to high comorbidity of anxiety and depression, and since escitalopram is frequently prescribed in anxiety disorders, we will explore severity of anxiety symptoms in all participants at baseline (V0), Week 4 (V1) and Week 8 (V2) of the treatment by using clinician reported Hamilton anxiety rating scale (HAM-A). Severity of anxiety symptoms will be compared between two test groups at two time points (V1 and V2) using mixed analysis of covariance (Mixed ANCOVA). Variables to be considered as covariates will be: Baseline HAM-A score (V0), Childhood trauma questionnaire score at V0, Age, Sex (Male=0, Female=1), Smoking status (0=Non-smoker, 1=Smoker), Alcohol consumption (0=No, 1=Yes), Metabolic syndrome (0=No, Yes).

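### The hypothesis 4 model is to be validated against TDM with no separate data, cross-validation or bootstrap named; done as written, its reported accuracy would on average be too high for patients not yet treated

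*Combined protocol and SAP*

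**What the plan says.** Hypothesis 4 (Hypotheses section) claims that the choice between standard and personalized dosing, and the size of any adjustment, "could have been determined before the beginning of the treatment using predictive model". The Secondary outcomes section of the SAP gives the aim as to "build model that could predict optimal dose for every patient even before the initiation of the treatment". Once all participants have finished, the investigators will "retrospectively build model using data collected during the trial, and then validate our model comparing it to the TDM method of dose personalization".

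On the model itself, the SAP says "Multiple linear regression model will be build using selected variables". The dependent variable is the week 2 (Vk) plasma concentration. The predictors are body mass index, creatinine clearance, AST/ALT ratio and four genotype indicators: "PM status (0=Yes, 1=No), IM status (0=Yes, 1=No), NM status (0=Yes, 1=No), UM status (0=Yes, 1=No". For this purpose all patients are genotyped and "divided into 4 groups based on the enzymatic capacity of CYP2C19 enzyme".

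Under Test groups, the TDM decision also rests on the week 2 concentration, with a window of 25 to 50 ng/ml. Under Secondary outcomes the plan expects that "about 40% of patients are expected to have their plasma escitalopram concentrations under the lower limit of the therapeutic window" and that "for about 10% of patients we expect to have plasma escitalopram levels above the upper limit of the therapeutic window".

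No section names a hold-out sample, external cohort, cross-validation, bootstrap or optimism correction, or says how agreement with TDM is to be measured. The retrospective data on 2087 patients are cited only for the expected shares outside the window.

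**The concern.** Hypothesis 4 is about patients who have not started treatment, so none of them can be in the data used to fit the model. Least squares chooses the coefficients that best fit the patients at hand. Scoring the model on those patients credits it with having fitted their noise, and the expected score exceeds the expected score in new patients. The later plasma samples at V1 and V2 come from the same people and so are not independent test data.

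At stake is the accuracy that readers would attach to a pre-treatment, genotype-based alternative to TDM. The plan calls this step validation, so the figure would be read as applying to future patients.

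**Working it through.** **No figure to reproduce.** The documents give no sample size, target R-squared or agreement figure for this model. Sample size (N) and true R-squared below are therefore assumptions, shown over a range.

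**1. Reference point from the plan's own figures.** With 40% below and 10% above the window, calling every patient 'within' agrees with TDM in about 100 − 40 − 10 = 50%.

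**2. Calibrating the concentrations.** The normal quantiles for 0.40 and 0.90 are −0.2533 and 1.2816.
- Normal: SD = (50 − 25) / (1.2816 + 0.2533) = 16.3 and mean = 25 + 0.2533 × 16.3 = 29.1 ng/ml. About 3.7% of values are negative, which is unrealistic in the lower tail.
- Lognormal: log-scale SD = ln(50/25) / 1.5349 = 0.452 and log-scale mean = 3.333. This was run as well because of the negative values.

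**3. Hand check of the R-squared bias.** The model has p = 6 estimable slopes: three continuous predictors and three genotype contrasts. For normally distributed predictors:
- same patients, approximately: 1 − (1 − R²)(N − p − 1)/(N − 1)
- new patients: 1 − (1 − R²)(N + 1)(N − 2)/[N(N − p − 2)]

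With assumed R² = 0.30:

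| N | Same patients | New patients | Difference |
|---|---|---|---|
| 50 | 1 − 0.7 × 43/49 = 0.386 | 1 − 0.7 × (51 × 48)/(50 × 42) = 0.184 | 0.20 |
| 100 | 1 − 0.7 × 93/99 = 0.342 | 1 − 0.7 × (101 × 98)/(100 × 92) = 0.247 | 0.10 |
| 200 | 1 − 0.7 × 193/199 = 0.321 | 1 − 0.7 × (201 × 198)/(200 × 192) = 0.274 | 0.05 |

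A simulation with normal predictors gave 0.38 vs 0.18, 0.34 vs 0.25 and 0.32 vs 0.27.

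**4. Simulated agreement with the TDM class.** The model had an intercept, three continuous predictors and three genotype indicators. Assumed allele frequencies were 15% for `*2` and 20% for `*17`, with `*2/*17` placed in the intermediate group for the simulation only. There were 1000 trials per setting, each also scored on 100,000 new patients. Results for assumed R² = 0.30, in %:

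| N | Concentrations | Same patients | 10-fold cross-validation | New patients | Same − new |
|---|---|---|---|---|---|
| 50 | normal | 63.6 | 57.4 | 57.3 | 6.3 |
| 50 | lognormal | 62.3 | 57.1 | 56.6 | 5.7 |
| 100 | normal | 61.9 | 58.7 | 58.9 | 3.0 |
| 100 | lognormal | 60.6 | 57.8 | 57.9 | 2.7 |
| 200 | normal | 61.1 | 59.5 | 59.8 | 1.3 |
| 200 | lognormal | 59.8 | 58.5 | 58.6 | 1.2 |

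Over R² 0.20 to 0.40 and both distributions:
- Agreement is overstated by 5.1 to 6.4 points at N=50, 2.6 to 3.2 at N=100 and 1.2 to 1.6 at N=200.
- R-squared is overstated by 0.18 to 0.25, 0.08 to 0.14 and 0.04 to 0.07.

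Cross-validation recovers new-patient agreement within 0.5 point, and its R-squared is 0.01 to 0.04 too low. Bootstrap correction stays 0.2 to 1.0 point and 0.01 to 0.06 in R-squared too high, most at N=50.

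**5. Does the model appear to beat calling everyone 'within'?** Any excess counts as a win.
- No signal: same-patient testing says yes in about 62% to 71% of trials at N=50 and 36% to 59% at N=200. Cross-validation says yes in about 20% to 26% over both sizes.
- R² 0.20 to 0.40, N=50: the fitted model truly is better in new patients in 95% to 100% of trials. Same-patient testing says so in 87% to 99% and cross-validation in 58% to 87%.
- R² 0.20 to 0.40, N=200: same-patient testing says so in 98% to 100% and cross-validation in 93% to 100%.

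**6. Genotype coding (separate, minor).** Four alleles give 4 × 5/2 = 10 allele pairs. The four groups list eight; `*2/*17` and `*3/*17` are missing. Once every patient is classified, the four indicators sum to a constant, so the intercept and seven predictors (8 columns) have rank 7. Individual genotype coefficients are then undefined, while fitted values are unchanged.

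**The case against.** The best defence is that the plan leaves the validation method open and does not prescribe a wrong one. That is correct. A reader might infer that the plan commits to same-patient testing or rules out internal validation; the text does neither. The bias follows only if nothing is added to what is written, and then only on average.

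A reader might also call the comparison circular because the week 2 concentration is both the fitted outcome and the basis of the TDM decision. It is the proper reference for a model meant to replace that measurement. The fault lies in reusing the patients.

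A third tempting inference is that the conclusion on hypothesis 4 would probably be wrong. The no-signal results alone suggest this, but the plan's premise is that CYP2C19 drives variability in escitalopram metabolism. At R² 0.20 to 0.40, the yes/no answer on beating the 'within' rule is usually right either way, and at N=50 same-patient testing is right more often than cross-validation. That criterion is also weak, since one patient can decide it, and the plan does not propose it.

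On size, the agreement bias is below one trial's sampling SD, √(0.5 × 0.5/N), which is about 7 points at N=50 and 3.5 at N=200. Listing the predictors in advance limits the optimism. Both points stand and restrain the weight given to this concern. Neither removes it: sampling error falls either way, whereas this bias favours the model, and no stated sample size makes it negligible.

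**Conclusion.** The concern holds as a gap that should be closed. That no validation method is named is certain from the text. If the same patients are used for fitting and testing, the upward direction of the bias on average is also certain. Its size is not: it rests on assumed N, R-squared, allele frequencies and concentration distributions. Within those assumptions it is material at about 100 patients or fewer and small by 200.

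The main consequence is an overstated accuracy figure for patients not yet treated. A worthless model passing as useful is a further risk only if the predictors carry little or no signal. This is a secondary, retrospective model, and the primary HAM-D and UKU analyses do not depend on it.

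**What to change.** State in the SAP that the model will be validated by cross-validation, preferably repeated, with every modelling step redone in each fold. Report the corrected agreement with the TDM below/within/above class and the corrected R-squared, both with confidence intervals, beside the agreement from calling every patient 'within' in the same patients. Bootstrap optimism correction is acceptable, with a note that it leaves some optimism at small N. Class agreement addresses whether to adjust; it does not by itself test the part of hypothesis 4 on how to adjust, so the SAP should also say what comparison will address that part.

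Separately and minor: before analysis, assign `*2/*17` and `*3/*17` to a stated metabolizer group, and enter three metabolizer indicators instead of four.

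The cost is a few lines of text and a short extra analysis of data already planned, with no new visits or samples. The downside is a lower reported accuracy.
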